**The Effect of Synbiotic Tablet Usage on the Clinical and Biochemical
Parameters in Smokers and Nonsmokers with Gingivitis: A Randomized
Placebo-Controlled Clinical Trial**

Document Date: February 27, 2018

Study Design

This study designed as a double-blind randomized placebo-controlled clinical trial.

Participants were primarily divided into two groups according to their smoking and non-smoking status. Then both groups in itself were randomly assigned again into two groups as test and control groups. Randomization was performed by one researcher that had never any role in participant's treatment and clinical measurement processes ([name]). Random selection was made in first person's participation by coin toss and then next participant was included into the other group according to previous participant's group. Four groups in this study are shown below:

- Smoker(+), test group(T) given synbiotic tablets; (T(+))
- Smoker(+), control group(C) given placebo tablets; (C(+))
- Non-smoker(-), test group(T) given synbiotic tablets; (T(-))
- Non-smoker(-), control group(C) given placebo tablets; (C(-))

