In the screening phase, clinical measurements were carried out as an initial evaluation and in the next visit biochemical and microbiological samples were collected for baseline examination and all participants were received mechanical debridement procedure including tooth-polishing (rubber-cup and abrasive paste) and scaling by the help of ultrasonic devices §§ and periodontal hand pieces ¶¶ before the experimental period. On the day of periodontal treatment each subject was instructed to chew one test or placebo tablet that was given according to their groups, per day, during 30 days. Test and placebo tablets were prepared to have the same characteristics in terms of shape, color, taste and size. Commercially available Probiotic Chewable Tablets ¶¶ (Table 1) were used in the test group and a placebo tablet had been prepared to same company with similar content with the test tablets but does not contain microorganisms. Oral hygiene training with tooth brush and floss was given to all participants. They were also instructed not to take other probiotic products throughout the test period. Clinical parameters including PI (28) and GI (29) and GCF samples had been obtained from all subjects on days 0 (baseline), 30 (1st month), and 60 (2nd month). Patients' professional supragingival plaque control was made in the control session of 1st and 2nd month. Side effects were recorded by patients'

verbal statement. Patients' all measurements and treatments were made by a single researcher who doesn't know in which group participants were included ([name]).

Biochemical Analysis

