**Document Date: February 27, 2018**

## Statistical Analysis

The suitability of the normal distribution of the variables in our study was evaluated with graphical and Shapiro-Wilks test. The median (minimum, maximum) was used to display the descriptive statistics of variables identified as an abnormal distribution. Number (n) and percentage values were given to show the distribution of categorical variables like gender.

Kruskal-Wallis non-parametric analysis of variance was used to examine if there has been any discrepancy in the values of the clinical and biochemical measurements at baseline, 1st month and 2nd month. Bonferroni correction with the dual comparisons were made to determine the group causing variations in the variables found significant differences as result of Kruskal-Wallis test.

For comparing the clinical, biochemical and microbiological measurements at baseline, 1 month and 2 months in each group (T(+) T(-), C(+), C(-)) Friedman non-parametric repeated measures analysis of variance was used. Bonferroni correction double comparisons were made in variables determined statistically significant differences from the result of the Friedman test.

G\*Power pack program\*\*\* was used in order to determine the number of samples used in the study. For the width effect f: 0.25, type-I error probability  $\alpha$ :0.05, type-II error probability  $\beta$ : 0.05 and power: 0.95, at least 15 sampling units have been calculated to include in the study for each group. At least 5 subjects were added for each group considering the missing data that was deemed to occur during the course of follow-up. Sample size calculation was attempted based on the primary outcome measure.

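### The SAP names no synbiotic-versus-placebo contrast and no baseline adjustment, and its indirect route to a treatment comparison has low power for modest effects

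*SAP*

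**What the plan says.** **Design (Protocol, Study Design).** "Participants were primarily divided into two groups according to their smoking and non-smoking status". Within each stratum the first participant was allocated "by coin toss and then next participant was included into the other group", and so on alternately. This gives four groups: T(+), C(+), T(-) and C(-). Plaque index, gingival index and gingival crevicular fluid are obtained at days 0, 30 and 60. Before the tablets start, "all participants were received mechanical debridement procedure", and everyone receives oral hygiene training.

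**Between groups (SAP, Statistical Analysis).** Kruskal-Wallis is used to look for "any discrepancy in the values of the clinical and biochemical measurements at baseline, 1st month and 2nd month". The grouping factor is not stated. After a significant result, "Bonferroni correction with the dual comparisons were made to determine the group causing variations in the variables". Neither the pairs nor the Bonferroni divisor is given.

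**Within groups (same section).** "For comparing the clinical, biochemical and microbiological measurements at baseline, 1 month and 2 months in each group", the SAP uses Friedman tests, again with Bonferroni comparisons.

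**Sample size (same section).** The SAP gives f = 0.25, alpha 0.05, power 0.95 and at least 15 per group, and then: "At least 5 subjects were added for each group considering the missing data". It refers to a primary outcome without naming it.

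The section names no T(+) versus C(+) or T(-) versus C(-) comparison, no pooled T versus C contrast, no treatment-by-smoking interaction, no change score and no baseline covariate.

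**The concern.** Treatment is what the trial allocates; smoking is a characteristic that participants bring with them. The allocated question is therefore T versus C, in each stratum or across both. The SAP reaches it only indirectly, through an omnibus test that responds to any difference among the groups, and then through pairs that the reader has to guess.

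Two things are at stake. First, a significant omnibus result on its own says nothing about the synbiotic, because a smoking difference is enough to produce it. Second, making each T-C pair pass an omnibus gate and then a multi-pair correction, while leaving the collected baseline values out of the comparison, may discard power that a trial of 15 to 20 per group cannot spare.

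**Working it through.** **1. The plan's own figure.** Inputs from the SAP: f = 0.25, alpha = 0.05, power 0.95, 15 per group, so N = 4 × 15 = 60. Assumed: a repeated-measures group-by-time interaction with k = 4 groups, m = 3 visits, correlation 0.5 and sphericity.

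- λ = f²·N·m/(1 − ρ) = 0.0625 × 60 × 3/0.5 = 22.5
- df1 = (k − 1)(m − 1) = 6; df2 = (N − k)(m − 1) = 112
- Power = 0.954, so 15 per group is reproduced.

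The match is not unique: the within-subject time effect at correlation 0.3 also gives 15 per group. The SAP plans no group-by-time test. A one-way four-group comparison at one visit with f = 0.25 has power 0.32 at N = 60 and 0.42 at N = 80.

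**2. Does a smoking effect produce false T-C findings?** Simulation with no treatment effect and 15 per group. With a smoking shift of 0.5 SD, Kruskal-Wallis is significant in about 30% of trials; with 1 SD, in about 87%. T-C pairs significant after the gate stay at about 1% (six pairs) to 4% (two pairs).

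**3. Power for T versus C.** Assumed: normal data, d = 0.5 SD in both strata, no smoking effect, 15 per group, one outcome, one visit. ρ is the baseline-to-follow-up correlation. Success in the stratum rows means a significant T-C result in at least one stratum.

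| Analysis | Power |
|---|---|
| Plan, six pairs (0.05/6 each) | 13-14% |
| Plan, two pairs (0.025 each) | 22-24% |
| Stratum Mann-Whitney at 0.025, no gate | 28-29% |
| Stratum t-test at 0.025, no gate | 32-33% |
| Stratum tests at 0.025, baseline-adjusted, ρ = 0/0.3/0.5/0.7 | 31/35/40/55% |
| Pooled T-C, adjusted for smoking | 47-48% |
| Pooled T-C, adjusted for smoking and baseline, same ρ | 47/51/58/75% |

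Where the gain comes from at the stratum level: dropping the gate adds about 6 points, and t-tests in place of rank tests add about 4. Baseline adjustment takes 32.2/33.4/31.7/32.5% to 31.0/34.7/40.1/54.5%, which is −1/+1/+8/+22 points: nothing at ρ = 0 and a material gain only from about ρ = 0.5.

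*Check by formula (normal approximation).* One stratum pair at 0.025 has power 0.192; at least one of two is 1 − (1 − 0.192)² = 0.35, close to the simulated t-test. Pooled, 30 per arm: 0.5/√(2/30) = 1.936, and Φ(1.936 − 1.960) = 0.49. With ρ = 0.5 the residual variance is 1 − 0.25 = 0.75, so 1.936/√0.75 = 2.236 and Φ(0.276) = 0.61. Both are slightly above the simulated values, as expected at this sample size.

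**4. Sensitivity.**
- *No losses (20 per group), d = 0.5:* plan 20% or 32-33%; adjusted stratum tests 42/44/53/69%; pooled with baseline 59/63/72/87%.
- *Larger effect, d = 0.8:* plan 41-42% or 58-59% at 15 per group, and 59-61% or 76-77% at 20. At d = 1.0 with 20 per group: 83-84% or 93-94%.
- *Effect of 0.8 SD in smokers only, 15 per group, ρ = 0/0.5:* pooled with baseline 31/40%; two-pair plan about 36%; adjusted stratum tests 43/56%.
- *Lognormal data with rank methods, 15 per group, d = 0.5:* two-pair plan 22-23%; rank stratum tests with baseline 30/33/38/49%; pooled rank ANCOVA 45/49/56/70%. Ties in the index scores were not simulated.

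**The case against.** The strongest defence is that the plan does compare the arms. It does not stop at the omnibus test, and on the four-group reading the follow-up pairs include T(+) versus C(+) and T(-) versus C(-), both within a stratum. This stands. A reader might infer that mixing smoking with treatment biases or inflates the treatment comparison. The documents do not support that: false T-C pairs stay at about 1-4%, and the omnibus rejections in step 2 correctly detect a real smoking difference, which may be of interest because smoking status is in the trial's title.

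It is also fair that the pooled figures answer a different question from the stratum pairs and assume the same effect in both strata. Stratum-specific questions are legitimate here, and with an effect in smokers only, pooling shows no clear gain over the two-pair plan. Nor can the whole difference between the plan and the adjusted stratum tests be credited to baseline; part comes from the gate and part from rank versus parametric tests.

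The number of pairs is unknown. Six and two are both assumptions, and four (T-C in each stratum, smoking in each arm) would be as plausible and gives about 17%. That uncertainty is itself part of the problem.

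Two further readings go too far. It would be wrong to say the plan disregards baseline, since Kruskal-Wallis is applied to the baseline values too; what is absent is adjustment or a change score. And a reader might infer that efficacy is to be judged from within-arm Friedman results. The SAP says only that these tests compare visits within each group and bases no efficacy claim on them.

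**Conclusion.** The concern holds in a limited form. The SAP names no T versus C contrast, does not identify or count its pairs, and uses no baseline adjustment, although the design allocates treatment within strata and baseline is collected. The result is a loss of power and clarity, not invalid inference: T-C pairs remain valid so far as the coin toss followed by alternation is sound.

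For a 0.5 SD effect in both strata with 15 per group, the planned route succeeds in about 13-14% (six pairs) or 22-24% (two pairs) of trials. Keeping the same stratum questions, simpler or baseline-adjusted tests reach about 28% to 55%, depending on method and on ρ. Pooling reaches 47% to 75%, but only if the effect is common to both strata. The deficit shrinks for large effects. These figures rest on simulated normal data for one outcome at one visit, with ρ and the number of pairs assumed.

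A reader might also infer that the sample size was built on a group-by-time test that the SAP then omits. The arithmetic is compatible with that but does not establish it, because another calculation gives the same 15.

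**What to change.** - Make the efficacy analysis a T versus C comparison adjusted for the baseline value (rank ANCOVA if the data are skewed), either within each smoking stratum at 0.025 each, or pooled with adjustment for stratum.
- State which of the two is primary, and for which outcome and visit. Pooling loses power if the effect is confined to one stratum.
- Keep the four-group Kruskal-Wallis as secondary, with its groups, its pairs and the Bonferroni divisor named.
- State that no efficacy claim rests on the within-arm Friedman tests. Every arm is debrided, so improvement over time is expected without any synbiotic effect.
- Both documents are written largely in the past tense. If results are already known, label the adjusted analysis as post hoc.

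The cost is SAP wording and one model per outcome. Baseline values and smoking stratum are already recorded, so no new data are needed.

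### If all pairs are meant, Bonferroni after a significant Kruskal-Wallis or Friedman test is valid but stricter than 5% family-wise control needs; Holm gives the same guarantee with more power

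*SAP*

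**What the plan says.** The SAP (Statistical Analysis) has two parallel rules.

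- **Between groups.** Kruskal-Wallis comes first. Pairs are then examined only "in the variables found significant differences as result of Kruskal-Wallis test", and the adjustment reads "Bonferroni correction with the dual comparisons were made to determine the group causing variations in the variables found significant differences".
- **Within each group, over visits.** Friedman comes first, and then "Bonferroni correction double comparisons were made in variables determined statistically significant differences from the result of the Friedman test".

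Neither sentence gives a divisor, lists the pairs or names the pairwise test. The protocol (Study Design) says "Four groups in this study are shown below" and lists synbiotic (T) and placebo (C) arms in smokers and in non-smokers. It measures at baseline, 1 month and 2 months. The only planning effect is in the SAP's sample-size paragraph ("For the width effect f: 0.25, type-I error probability" and so on), which arrives at 15 per group plus 5 for missing data. No pairwise difference or pairwise power is given.

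**The concern.** A pair can be declared different only if it passes two hurdles: a 5% omnibus test, and then a Bonferroni threshold. With all pairs in the family, that threshold is 0.05/6 between groups and 0.05/3 between visits. The omnibus test already protects the case in which nothing differs, and once something does differ, not every pair can still be equal. Full Bonferroni therefore guards against more true null hypotheses than can exist at that point.

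What is at stake is power. The SAP names no test of synbiotic against placebo other than the pairs that follow Kruskal-Wallis. With 15 to 20 per group, those tests have limited power to begin with.

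**Working it through.** **1. The plan's own figure.** Fifteen per group reproduces as a repeated-measures group-by-visit interaction with f = 0.25, α = 0.05, 4 groups and 3 visits, assuming correlation ρ = 0.5 and sphericity. The noncentrality is λ = f²·N·m/(1−ρ). At N = 60 this is 0.0625 × 60 × 3 / 0.5 = 22.5, with 6 and 2 × (60 − 4) = 112 degrees of freedom, and power is 0.954. The smallest sufficient N is 59, or 15 per group. The result depends on ρ: 21 per group at 0.3 and 10 at 0.7. Of the other tests tried, one-way ANOVA needs 70 per group, the repeated-measures between factor 47 and the within factor 11. The planned 95% power thus fits an omnibus interaction test and says nothing about pairs.

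**2. Divisors if all pairs are meant (assumption).** Four groups give 4 × 3/2 = 6 pairs, so 0.05/6 = 0.0083. Three visits give 3 × 2/2 = 3 pairs, so 0.05/3 = 0.0167.

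**3. How many pair nulls can be true.** If all groups are equal, a false pairwise claim first needs a false omnibus result, which is held at 5%. If they are not all equal, the most true pair nulls arise with three groups alike and one different: 3 of 6. For visits the maximum is 1 of 3. So 0.05/3 for group pairs and 0.05 for visit pairs suffice behind the omnibus test, provided each pair has its own rank-sum or signed-rank test.

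**4. Family-wise error, group pairs.** Simulation: Kruskal-Wallis at 0.05, then two-sided rank-sum pairs, on normal data with equal SDs. The second column has one group shifted by 1 SD or more.

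| Pair threshold | One group differs | All equal, n = 20 |
|---|---|---|
| 0.05 | 0.117–0.123 | 0.047 |
| 0.05/3 | 0.037–0.042 | 0.044 |
| 0.05/6 | 0.018–0.020 | 0.032 |

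The highest value in any simulation with 0.05/3 was 0.048.

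**5. Power for one synbiotic-placebo pair.** Same simulation, same shift in both strata.

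| n per group | Shift | 0.05/6 | 0.05/3 | Gap (points) |
|---|---|---|---|---|
| 15 | 0.5 SD | 8% | 11% | 3 |
| 15 | 0.8 SD | 24% | 33% | 9 |
| 15 | 1.0 SD | 42% | 53% | 11 |
| 15 | 1.5 SD | 85% | 91% | 6 |
| 20 | 0.5 SD | 11% | 16% | 5 |
| 20 | 1.0 SD | 60% | 71% | 11 |

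At n = 15 and 1 SD, Holm gives about 46%. As a check without the omnibus step, a two-sample t test with n = 15 and d = 1 has noncentrality 1 × √(15/2) = 2.74 on 28 df. Its power is 58% at 0.05/3 and 47% at 0.05/6, again 11 points.

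**6. Visit pairs.** Friedman at 0.05, then signed-rank pairs, ρ = 0.5 assumed. Behind Friedman, the highest simulated error was 0.049 at an unadjusted 0.05 and 0.023 at 0.05/3. With one visit 0.7 SD from the other two, power is 54% against 41% at n = 15 (13 points) and 71% against 60% at n = 20 (11 points).

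**7. Why Holm cannot lose to Bonferroni.** Holm compares the ordered p-values with 0.05/m, 0.05/(m−1), …, 0.05. For m = 6 these are 0.0083, 0.0100, 0.0125, 0.0167, 0.0250 and 0.0500. No threshold is below Bonferroni's, and family-wise error stays within 5% for any pattern of true nulls and any m.

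**The case against.** **Nothing is invalid.** An omnibus test followed by Bonferroni is a legitimate, conservative procedure, and choosing a sharper one is a preference about efficiency. That stands.

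**The divisor is inferred.** If only T(+) against C(+) and T(-) against C(-) are compared, Bonferroni is 0.05/2 = 0.025, and a fixed 0.05/3 would be stricter than the SAP's rule. That also stands. It limits the 0.05/3 option to the six-pair reading, but it does not touch Holm.

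**A reader might infer that the Bonferroni step buys no error control and could be dropped.** The documents do not support this. With four groups the omnibus test alone does not protect the pairs (about 0.12 unadjusted), and dividing by 6 lowers the actual error to about 0.02, against about 0.04 with 0.05/3. The narrower statement holds: a 5% limit does not require 0.05/6.

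**A reader might also take about 10 points as the general cost.** It is a mid-range figure. In a two-against-two pattern f = d/2, so a 1 SD effect is f = 0.5. Reading the SAP's f = 0.25 as a between-group effect in that pattern (an assumption) gives d = 0.5, where the gap is 3 to 5 points.

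**Relaxing the visit comparisons is not free.** The SAP has no correction across outcomes, groups or visits. With 5% allowed in each of four groups, the chance of at least one false visit pair per variable can reach 1 − 0.95⁴ = 19%. The 5% guarantee under Bonferroni is also per group only, but its actual error is lower. This trade-off is real for the unadjusted visit option.

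**Conclusion.** The point holds as an efficiency improvement. If all pairs are meant, both sentences are stricter than 5% family-wise error needs, where the family is one variable at one visit for the group comparison, and one variable in one group for the visit comparison. At 15 per group and a 1 SD effect in both strata, power per synbiotic-placebo pair is about 42% as written, 46% with Holm and 53% with 0.05/3 behind the omnibus test. The gap narrows for small and for large effects.

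One further inference should be resisted: that the Friedman sentence hides synbiotic effects. Its pairs show change within a group, and every group received debridement, so any gain there is not a gain for synbiotic against placebo.

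Assumptions: the Kruskal-Wallis factor is the four groups at each visit; all pairs are tested, two-sided, by separate rank-sum or signed-rank tests; data are normal with equal SDs; the correlation between visits is 0.5. The counting argument and the Holm comparison do not depend on the normality, SD or correlation assumptions; the power figures do.

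**What to change.** State which pairs are compared and by which test, and replace Bonferroni with Holm over that set in both sentences. This costs two sentences, with no new data or patients. Every Bonferroni rejection is kept, with the same 5% guarantee, whatever the number of pairs.

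Optional, only if all six group pairs are tested by separate rank-sum tests: use a fixed 0.05/3 per pair after a significant Kruskal-Wallis test, and test the three visit pairs at 0.05 by separate signed-rank tests after a significant Friedman test. Describe the group rule as an omnibus-first threshold, not as the ordinary Shaffer procedure, which starts at 0.05/6. The price is a higher actual error, still within 5% for each family as defined above, but with no control across groups, visits or outcomes; the SAP should say so. Between-group pairs should not be left unadjusted.

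### The stated 95% power matches only repeated-measures F-tests that the SAP does not plan, so it is not the power of the planned analysis, least of all of synbiotic versus placebo

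*SAP*

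**What the plan says.** The sample size paragraph of the SAP (Statistical Analysis) gives f = 0.25, alpha 0.05, beta 0.05 and power 0.95, and states that "at least 15 sampling units have been calculated to include in the study for each group". It continues: "At least 5 subjects were added for each group considering the missing data", which makes 20 per group and 80 in all. It adds: "Sample size calculation was attempted based on the primary outcome measure". The paragraph does not say which G*Power procedure was used, which effect f measures, or what correlation between repeated measurements was entered.

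The same section sets out the tests:
- Between groups, for each of the three visits: "Kruskal-Wallis non-parametric analysis of variance was used to examine if there has been any discrepancy in the values of the clinical and biochemical measurements". Pairs follow: "Bonferroni correction with the dual comparisons were made to determine the group causing variations".
- Within each of the four groups, over the three visits: "Friedman non-parametric repeated measures analysis of variance was used", again followed by Bonferroni pairs.

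The Protocol (Study Design) first splits participants by smoking status; then "both groups in itself were randomly assigned again into two groups as test and control groups". Tablets are "given according to their groups, per day, during 30 days", measurements are taken on days 0, 30 and 60, and everyone has debridement before the tablets start.

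**The concern.** A reader will take 95% as the chance that the trial detects its target effect. That holds only if the test behind the calculation is among the tests to be run, and the settings that return 15 per group are tests absent from the plan.

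The comparison that carries the trial's question is synbiotic (T) against placebo (C) within a smoking stratum. The plan reaches it directly only through Bonferroni pairs after Kruskal-Wallis. Friedman cannot stand in for it: a change over time within one group does not isolate the synbiotic when every participant was also debrided. No planned test examines whether groups change differently over the visits. At stake is whether a null result on T versus C may be read against a 95% figure that was never calculated for it.

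**Working it through.** **Inputs.** From the SAP: f = 0.25, alpha 0.05, 15 per group (20 with the allowance). From the Protocol: k = 4 groups, m = 3 visits. Assumed, because the documents give none: correlation rho, sphericity, normal data, mean patterns. Also assumed: six pairs (all pairs of four groups) compared by Mann-Whitney, since the SAP gives neither the number of pairs nor the pairwise test.

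**Step 1: reproduce the 15.** For a repeated-measures visit or interaction F-test, λ = f²·N·m/(1−rho) and df2 = (N−k)(m−1); df1 is m−1 (visit) or (k−1)(m−1) (interaction). For the 4 × 3 interaction at rho 0.5:
- N = 56: λ = 0.0625 × 56 × 3/0.5 = 21.0, df 6 and 104, power 0.937.
- N = 60: λ = 0.0625 × 60 × 3/0.5 = 22.5, df 6 and 112, power 0.954.
- N = 80: λ = 30.0, df 6 and 152, power 0.992.

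So 15 is the smallest equal group size that reaches 0.95. The arithmetic of the plan is sound for this test.

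**Step 2: which other F-tests give 15?** Rho was scanned from 0 to 0.995 in steps of 0.005. These ranges have 15 per group as the minimum:

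| Groups | Effect | Three visits | Two visits |
|---|---|---|---|
| 4 | interaction | 0.49–0.525 | 0.595–0.62 |
| 4 | visit | 0.295–0.335 | 0.445–0.48 |
| 2 | interaction or visit | 0.66–0.675 | 0.735–0.75 |
| 1 | visit | 0.84–0.845 | 0.88–0.885 |

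Between-group F-tests never give 15. With λ = f²·N·m/(1+(m−1)rho), four groups need at least 24 per group (three visits) or 36 (two visits), both at rho 0. A one-way F with λ = f²·N needs 70 per group; at 15 per group λ = 0.0625 × 60 = 3.75 and power is 0.317.

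**Step 3: the planned tests under the interaction that gives 15.** Take interaction f = 0.25, rho 0.5, SD 1 and equal baselines. The T−C difference d at the visit with the full effect solves d²·Vt·Vg = 0.0625. Here Vt is the variance of the time pattern: 2/9 for a flat effect (0, 1, 1), and 1/6 for linear growth (0, 0.5, 1) or a day-30 peak (0, 1, 0.5). Vg is the variance of the group pattern: 1/4 if both strata share the effect, 3/16 if one group is shifted, 1/8 if T and C in one stratum are opposite extremes.
- Flat: 0.25/√(2/9 × 1/4) = 1.06; likewise 1.22 and 1.50 SD.
- Linear or peak: 0.25/√(1/6 × 1/4) = 1.22; likewise 1.41 and 1.73 SD.

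Simulated power (60,000 runs per cell; T versus C at 0.05/6, listed for the three group patterns in that order):

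| Test | Effect | 15 per group | 20 per group |
|---|---|---|---|
| Interaction F (not planned) | either | 95% | 99% |
| Kruskal-Wallis, each follow-up visit | flat | 91–92% | 97–98% |
| Kruskal-Wallis, best visit / other visit | linear or peak | 97% / 43% | 99.6% / 57% |
| T versus C, one stratum | flat | 48, 64, 85% | 66, 81, 96% |
| T versus C, one stratum, best visit | linear or peak | 64, 79, 95% | 81, 93, 99% |

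The exact Mann-Whitney test changes the T-versus-C figures by at most 2 points; requiring a significant Kruskal-Wallis first, or using Dunn's test, changes them by at most 3. If only the two T-versus-C pairs are corrected, the flat figures at 15 per group become about 66, 79 and 93%.

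The linear and peak patterns matter because the tablets stop at day 30 and the last measurement is a month later; nothing in the documents fixes a flat effect.

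**Step 4: the same f read differently.** If f = 0.25 means a group effect at one visit, Kruskal-Wallis has about 29% at 15 per group and 39% at 20 (20,000 runs), and needs about 73–74 per group for 95%.

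**The case against.** The strongest reply is that the planned omnibus test roughly delivers the stated power. With equal baselines, Kruskal-Wallis has 91–97% at its best follow-up visit with 15 per group. As no adjustment across visits is stated, it rejects at one or both follow-up visits in 97–98% of simulated trials (over 99% at 20 per group). This stands for Kruskal-Wallis under that reading of f, at the price of unadjusted type I error. It does not carry over to the T-versus-C pairs.

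Second, sizing a rank test from its parametric counterpart is an accepted approximation, and the single-group, three-visit F-test at rho 0.84 is the counterpart of the planned Friedman test. There Friedman has 85–86% at 15 and 95–96% at 20. This also stands. A reader might quote the Friedman powers of 28% and 38% found at rho 0.3 and 0.5 as the shortfall. They should not be used so: they take f as a visit effect in one group, at correlations where 15 is not the solution.

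Third, the search covered F-tests only, so the match is exclusive among F-tests and no wider. The six-pair correction is likewise an assumption, which is why the two-pair figures are given.

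A reader might go further and infer that 15 is a miscalculation, that the trial is too small, or that no primary outcome is named. The documents support none of these. The 15 reproduces, power is above or below 95% depending on a mean pattern that is not stated, and part of the SAP is absent from the available text, so the outcome may be named there.

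**Conclusion.** The point holds in this form: the 95% belongs to an unnamed F-test and is not the power of the planned analysis. Which F-test it was cannot be told from the text. For synbiotic versus placebo within a smoking stratum, the interaction that gives the F-test 95% gives about 48–85% (flat) or 64–95% (linear or peak, best visit) at 15 per group, and about 66–96% or 81–99% at 20, with six pairs corrected. Kruskal-Wallis ranges from about 29% to 97% at 15 per group, according to what f means, which visit is tested and how the effect evolves.

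These figures rest on normal data, sphericity, rho 0.5 where an interaction is assumed, equal baselines and the listed patterns. They show how far the answer moves; they do not fix the trial's true power. The matter is worth correcting because the SAP attaches an unqualified figure to a plan whose only direct test of the treatment has no calculated power.

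**What to change.** 1. State the G*Power test, the effect f refers to, the correlation, the sphericity assumption and the outcome entered, and say that the 95% applies to that F-test only.
2. Restate power for the planned tests at 15 and 20 per group, above all for the Bonferroni T-versus-C comparison, conditional on stated mean patterns, correlation, pairwise test and number of pairs.
3. If the interaction was the powered test, a group-by-visit test on the primary outcome may be added. The SAP is written in the past tense, so date it and label it as added later. At f = 0.25 its power is 85%, 95% and 99.8% with 60 participants for rho 0.3, 0.5 and 0.7, and 95%, 99% and over 99.9% with 80. It assumes normality, and its 6 degrees of freedom also pick up smokers and non-smokers responding differently over time. Support it with T-versus-C-by-visit contrasts within each smoking stratum; the powers just quoted do not apply to those contrasts. If another test was powered, items 1 and 2 suffice.

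The cost is SAP wording, retrieval of the G*Power inputs, a modest simulation and at most one added model. No extra patients are needed. The downside is a power statement that is conditional and less favourable, and possibly a test labelled as later than the original plan.
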